**Renal Cortex (right and left combined as one)**

Specifically, the parallel functioning nephrons of the renal cortices of the kidneys (not the hilum).

**Liver**

The entire liver minus the GTV targets.

**Bile ducts**

May use the portal vein from its juncture with the splenic vein to its right and left bifurcation in the liver as a surrogate to identify the bile ducts.

**Other Structures**

The constraints tables above contain other structures. These are required if the structure is within 10 cm of the PTV.

## **4.8 SABR Compliance**

### **4.8.1 Dosimetry Compliance**

RT treatment plans not meeting the “per protocol” criteria or scored as “variation acceptable” will be classified as “deviation unacceptable.” Normal tissue dose constraints are listed above. **NOTE: For the spinal cord, these are absolute limits, and treatment delivery that exceeds these limits will constitute a major protocol violation.** For the non-spinal cord tissues, acceptable deviation following the planning priorities allows a maximum point dose no more than 105% of the prescription dose while fully respecting the defined volume constraint (for serial tissues) OR exceeding the parallel tissue critical volume dose maximum by no more than 5%. Unacceptable deviation exceeds the volume constraint for serial tissues, exceeds the maximum point dose for serial tissues by more than 105% of the prescription dose, or exceeds the parallel tissue critical volume dose maximum by more than 5%.

### **4.8.2 Contouring Compliance**

Accurate and appropriate contouring is essential for the generation of dose volume statistics. In addition, it is the desire of the investigator to compile a comprehensive database of dose volume information coupled with outcomes data (control/toxicity) in order to define accurate dose response effects. As such, we require that the tumor targets and normal tissues in the vicinity be contoured in all patients. In particular, any structure listed with a constraint in Critical Structures and residing within 10 cm in any direction from the PTV must be contoured. Appropriateness of contouring will be scored by the study PIs as either no deviation, minor deviation, or major deviation.

## **4.9 Toxicities and Dosing Delays/Dose Modifications**

Any subject who receives treatment on this protocol will be evaluable for toxicity. Each patient will be assessed for the development of toxicity according to the Time and Events table (See section 5.4). Toxicity will be assessed according to the NCI Common Toxicity Criteria for Adverse Events (CTCAE), version 4.0 and RTOG/EORTC acute and late toxicity criteria as described in <http://www.rtog.org/ResearchAssociates/AdverseEventReporting.aspx> and in Appendix B and C. Dose adjustments should be made according to the system showing the greatest degree of toxicity.

**4.10 Duration of Therapy**

No more than three SABR fractions will be delivered per week. Therefore the treatment duration will be between 2-3 weeks depending on the fractionation scheme chosen.

**4.11 Duration of Follow Up**

Subjects will be followed for 2-5 years with MRI scans every 6 months for the first year and if there is no growth then every six months subsequently; if there is evidence of growth, frequency will be determined by physician.

**4.12 Removal of Subjects from Protocol Therapy**

Subjects will be removed from therapy when any of the criteria listed in [Section 5.5](#) apply. Notify the Principal Investigator, and document the reason for study removal and the date the subject was removed in the Case Report Form. The subject should be followed-up per protocol.

**4.13 Subject Replacement**

The following are criteria for subject replacement: 1) If the subjects decide to withdraw from the study without finishing the course of SABR, 2) if the subjects decide to withdraw from the study or lost to follow up (for reasons of death from other causes, moving to other state etc.) or refuse follow up scans leading to <3 follow-up scans or <1 year of follow up, 3) if the subjects become unable to undergo an MRI or contrast enhanced CT scan with <1 year of follow up.

**5.0 STUDY PROCEDURES****5.1 Screening/Baseline Procedures**

Assessments performed exclusively to determine eligibility for this study will be done only after obtaining informed consent. Assessments performed for clinical indications (not exclusively to determine study eligibility) may be used for baseline values even if the studies were done before informed consent was obtained.

All screening procedures must be performed within two months prior to registration unless otherwise stated. The screening procedures include:

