2.4.3.3 To develop a 4D model of patient-specific tumor motion

### **3.0 SUBJECT ELIGIBILITY**

Subjects must meet all of the inclusion and exclusion criteria to be registered to the study. Study treatment may not begin until a subject is registered.

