3.1.3 Biopsy proven Renal neoplasm

3.1.3.1 All histology of renal cancers are included, including oncocytoma

3.1.4 Growth of renal mass  $>2$ mm in radiographic scans must be demonstrated within a one year period.

3.1.5 Ability to understand and the willingness to sign a written informed consent.

3.1.6 Subject is able to undergo either an MRI or administration of contrast agent for CT.

3.1.7 Women of child-bearing potential and men must agree to use adequate contraception (hormonal or barrier method of birth control; abstinence) for the duration of the study. Should a woman become pregnant or suspect she is pregnant while participating in this study, she should inform her treating physician immediately.

3.1.6.1 A female of child-bearing potential is any woman (regardless of sexual orientation, having undergone a tubal ligation, or remaining celibate by choice) who meets the following criteria:

- Has not undergone a hysterectomy or bilateral oophorectomy; or
- Has not been naturally postmenopausal for at least 12 consecutive months (i.e., has had menses at any time in the preceding 12 consecutive months).

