3.2.2 Subjects received previous abdominal radiation

- 3.2.3 Evidence of Metastatic Disease, unless disease-free for  $\geq 3$  years prior to registration, (non-melanomatous skin cancer and in-situ cancers are okay).
- 3.2.4 Female subjects who are pregnant or planning to become pregnant during the course of SABR.

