**5.1.13 Pregnancy test (for females of child bearing potential)**

Standard urine pregnancy test will be used to rule out pregnancy

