**5.2 Procedures during Treatment**

SABR treatment will be delivered either in three, four or five fractions. For a given lesion (target), a minimum of 40 hours and a maximum of 8 days should separate consecutive treatments. All treatment must be completed within 21 days.

**5.2.1 Prior to starting first SABR treatment: Baseline assessment is sufficient and need not be repeated if done within the past two months**

- Physical exam, vital signs

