**5.2.2 Day 1**

- First fraction of SABR
- Correlative Blood draw 1-2 hours after first SABR fraction only (see section 8).

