### 6.1.3 Methods for Evaluation of Measurable Disease

All measurements should be taken and recorded in metric notation using a ruler or calipers. All baseline evaluations should be performed as closely as possible to the beginning of treatment and never more than 28 days before the beginning of the treatment planning session.

The same method of assessment and the same technique should be used to characterize each identified and reported lesion at baseline and during follow-up. Imaging-based evaluation is preferred to evaluation by clinical examination when both methods have been used to assess the antitumor effect of a treatment.

Conventional CT with contrast: These techniques should be performed with cuts of 1 mm or less in slice thickness contiguously. Spiral CT should be performed using a 5 mm contiguous reconstruction algorithm.

MRI: Will be performed with gadolinium if possible. These techniques should be performed with cuts of 1 mm or less in slice thickness contiguously.

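### The only pregnancy test is timed to registration, not to treatment, so a compliant negative result can be weeks to months old when abdominal SABR starts

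*Protocol*

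**What the plan says.** Pregnancy is an exclusion under Protocol 3.2.4: "Female subjects who are pregnant or planning to become pregnant during the course of SABR". Section 5.1.13 supplies the check, for women of child-bearing potential: "Standard urine pregnancy test will be used to rule out pregnancy". It states no timing, so the default at the head of Section 5.1 governs: "All screening procedures must be performed within two months prior to registration unless otherwise stated". Section 3.0 fixes the order of events, "Study treatment may not begin until a subject is registered", but sets no longest interval between registration and treatment.

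Section 5.2.1 covers the period just before the first fraction and says: "Baseline assessment is sufficient and need not be repeated if done within the past two months". The only items listed under it are physical exam and vital signs. Section 5.2.2 (Day 1) lists "First fraction of SABR" and a correlative blood draw. Table 5.4 has no pregnancy-test row, and its pre-study column is also tied to registration.

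The other safeguards are contraception throughout the study and self-report under 3.1.7 ("Should a woman become pregnant or suspect she is pregnant while participating in this study, she should inform her treating physician immediately"), and removal under 5.5.7 of a woman who becomes pregnant before her SABR course is finished.

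**The concern.** The risk lies in irradiating a pregnant woman, so the date that matters is the date of simulation or first fraction. The Protocol ties its only objective check to registration, which comes earlier by an unspecified amount. A woman who conceives after the screening test and does not yet suspect it would pass every required step and go on to receive 36 to 40 Gy to a kidney tumour (4.2.2). Removal under 5.5.7 would then depend on her own report, because no scheduled test would reveal the pregnancy.

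Test timing is a protocol procedure rather than something normally left to a SAP. The weakness is in a window the Protocol does state, which has the wrong anchor.

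**Working it through.** The Protocol gives no figure for the age of the test at treatment, so there is none to reproduce. What can be worked out is the oldest negative result that still complies.

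**Inputs**
- Screening window: two months before registration (5.1). Two calendar months are 59 to 62 days, mean 60.9, taken as 61.
- Wait from registration to first fraction, *w*: at least 0 (3.0), with no upper limit stated. Values of 7, 14 and 28 days are assumed here for illustration.
- Two other limits that might be argued to apply: two months in 5.2.1, and 28 days before the planning session in 6.1.3.

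**Three readings**

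(a) *The 28-day limit in 6.1.3 covers the test.* That section says "All baseline evaluations should be performed as closely as possible to the beginning of treatment and never more than 28 days" before the planning session. Maximum age = 28 days at planning, plus a planning-to-treatment gap for which no limit is stated.

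(b) *The two-month limit in 5.2.1 covers the test.* Maximum age at first fraction = 61 days (59 to 62), or 61 / 7 = 8.7 weeks.

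(c) *Only 5.1 applies.* Maximum age at first fraction = 61 + *w*:

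| Assumed *w* (days) | Maximum age (days) | Range for 59 to 62-day months |
|---|---|---|
| 7 | 61 + 7 = 68 | 66 to 69 |
| 14 | 61 + 14 = 75 | 73 to 76 |
| 28 | 61 + 28 = 89 | 87 to 90 |

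**Which reading fits the text.** Section 6.1.3 concerns methods for measuring lesions and sits beside rules on calipers and slice thickness, so applying it to a urine test is a stretch. The allowance in 5.2.1 heads a list that contains only physical exam and vital signs. Reading (c) is therefore the most natural. The conclusion does not depend on that choice, since every reading permits a result at least four weeks old by planning or treatment.

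**Effect of a short window.** If a 7-day window (assumed) were tied to the same point, the maximum would fall from 28 to 7 days under (a), a gain of 21 days, and from 61 to 7 days under (b), a gain of 54 days. Under (c) it would replace an open-ended maximum with 7 days.

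**The case against.** The best defence is that nothing here is contradictory. The Protocol excludes pregnancy, tests for it, bars treatment before registration and applies one screening window throughout; a tighter window is a preference, and the document contains no standard that two months fails. Harm would need contraceptive failure or non-use after the test, without suspicion, in one of few eligible women among 16 participants. Sections 5.2.1 and 6.1.3 can be read as capping the age of baseline assessments, which would remove the 68 to 89-day figures. Those figures rest on assumed waits in any case, and all of them are ceilings. The missing row in Table 5.4 proves little, since the table also omits other required screening items such as demographics and concomitant medications. Finally, the remedy is partial: treatment may run for 21 days (5.2), so a test 7 days before the first fraction could be about 7 + 21 = 28 days old at the last.

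Much of this stands as to size. The event is unlikely, the figures are upper limits, the table gap is only supporting evidence, and conception during the course stays uncovered. It does not remove the point. Even on the readings most favourable to the Protocol, the test may be about four to nine weeks old around planning or treatment. Contraception, self-report and removal lower the risk without verifying status before the beam is turned on.

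**Conclusion.** The point holds as a minor patient-safety weakness. There is one pregnancy test, its window is anchored to registration, and no required step confirms status near simulation or first SABR. The oldest compliant negative result is 28 days at planning, about 61 days at first fraction, or about 61 days plus an unlimited wait, depending on the reading; the last is the most natural.

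The 68, 75 and 89-day figures assume waits of 1, 2 and 4 weeks that the Protocol does not give. A compliant test may well be done much nearer to treatment. The Protocol does not say how many participants will be of child-bearing potential; with 16 planned in total, few are likely. The primary endpoint, sample size and analysis are unaffected. The change is worth making because it is cheap and the harm it guards against is serious and avoidable.

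**What to change.** In 5.1.13, state that the urine test for women of child-bearing potential (as defined under 3.1.7) must fall within a short fixed window before simulation or the first SABR fraction, naming which. Seven days or less is offered as an example; the clinical team should set the value. A screening test inside that window suffices; otherwise it is repeated. Add the test as a bullet in 5.2.1 and as a row in Table 5.4.

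The cost is one sentence, one bullet and one table row, plus an occasional later or repeat urine test for the few women concerned. Conception during the course would still rest on contraception and self-report.

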**5.1.1 Informed Consent****5.1.2 Medical history**

Complete medical and surgical history, history of infections, history of previous cancers, history of previous radiation, family history of cancers.

**5.1.3 Demographics**

Age, gender, race, ethnicity

**5.1.4 Review subject eligibility criteria****5.1.5 Review previous and concomitant medications****5.1.6 Physical exam including vital signs, height and weight**

Vital signs (temperature, pulse, respirations, blood pressure), height, weight

**5.1.7 Performance status**

Performance status evaluated prior to study entry according to ECOG performance scale.

**5.1.8 Adverse event assessment**

Baseline adverse events will be assessed prior to the beginning of treatment. See section 7.0 for Adverse Event monitoring and reporting.

**5.1.9 Hematology**

CBC with differential

**5.1.10 Blood draw for correlative studies**

See Section 8.0 for details.

**5.1.11 Serum chemistries**

Comprehensive metabolic panel (CMP) to include: albumin, BUN, creatinine, electrolytes (sodium, potassium, calcium, chloride, bicarbonate), glucose, phosphate and calcium.

**5.1.12 Urine analysis**

Urine analysis including RBC, WBC, protein, creatinine, protein to creatinine ratio.

**5.1.13 Pregnancy test (for females of child bearing potential)**

Standard urine pregnancy test will be used to rule out pregnancy

**5.1.14 Biopsy of Renal lesion****5.1.14.1 Pre-treatment biopsy:**

A CT-guided biopsy of a tumor lesion will be performed prior to study registration, unless previous biopsy of the same lesion is performed within the last one year exists and a review of slides shows it to be adequate, in which case a pretreatment biopsy is optional.

**5.1.14.2 Post-treatment biopsy:**

A post-treatment biopsy will be performed at one year post treatment regardless of whether clinical indication (tumor growth >4mm, enhancement, etc.) is present or not.

**5.1.15 Tumor assessment**

Tumor assessment will be performed using MRI with (preferred) or without contrast, or contrast enhanced CT. A growth of >2mm of tumor size within one year period must be demonstrated to meet be eligible for this study.

**5.1.16 Kidney function assessment:**

Kidney perfusion assessed by Renal scintigraphy scan performed at baseline and at one year post treatment.

**5.2 Procedures during Treatment**

SABR treatment will be delivered either in three, four or five fractions. For a given lesion (target), a minimum of 40 hours and a maximum of 8 days should separate consecutive treatments. All treatment must be completed within 21 days.

**5.2.1 Prior to starting first SABR treatment: Baseline assessment is sufficient and need not be repeated if done within the past two months**

- Physical exam, vital signs

**5.2.2 Day 1**

- First fraction of SABR
- Correlative Blood draw 1-2 hours after first SABR fraction only (see section 8).

**5.2.3 4 weeks (+/-1 week) after treatment termination**

- Physical Exam: including: medical history and vital signs
- Hematology
- Serum chemistries
- Lab corollary blood draw
- Urine Analysis
- Performance status
- Toxicity evaluation

**5.3 Follow-up Procedures**

Subject will be followed at every six months (+/- 2 weeks) thereafter for five years after their first follow up at 1 month (+/- 1 week).

With every visit, patients will have:

- Physical exam including: vital signs, weight, height and BMI
- MRI with or without contrast or CT with contrast
- Renal scintigraphy scan at 1 year
- Hematology
- Serum Chemistries
- Urine Analysis
- Lab corollary blood draw at 1 month and six month
- Performance status
- Toxicity evaluation
- Tumor measurements

**\*Note:** Subjects who show progressive disease or develop a new primary will be followed for survival only and will no longer strictly adhere to study calendar.

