## **2.4 Endpoints**

### **2.4.1 Primary Endpoint:**

Local control of the SRMs will be defined as <4mm increase in the longest tumor diameter compared to pre-treatment scan on an MRI or contrast-enhanced CT scan in the setting of no radiographic or pathologic evidence of viable tumor.

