#### **6.1.4 Response Criteria**

##### **6.1.4.1 Evaluation of Lesions**

Complete Response (CR): Disappearance of all target lesions. Disappearance of all target lesions. Any pathological lymph nodes (whether target or non-target) must have reduction in short axis to <10 mm (the sum may not be "0" if there are target nodes). Determined by two separate observations conducted not less than 4 weeks apart. There can be no appearance of new lesions.

Partial Response (PR): At least a 30% decrease in the sum of the longest diameter (LD) of target lesions, taking as reference the baseline sum LD. There can be no appearance of new lesions.

Progressive Disease (PD): > 20% increase in the SLD taking as reference the smallest SLD recorded since the treatment started (nadir) and minimum 5 mm increase over the nadir.

Stable Disease (SD): Neither sufficient shrinkage to qualify for PR nor sufficient increase to qualify for PD, taking as reference the smallest sum LD since the treatment started. There can be no unequivocal new lesions.

Tumor Growth (TG): At least a 4mm increase in the LD of treated lesion in a single scan when compared to baseline scan (or an increase of >2.0mm in two consecutive scans).

Local Control: No TG AND a complete radiographic or pathologic absence of tumor viability.

Local Failure: Any TG OR any radiographic or pathologic evidence of tumor viability.

Indeterminate Disease Response: (IDR): 1) Presence of radiographic evidence of viable disease without any increase in the LD (<4mm) sufficient enough to qualify for TG; 2) complete absence of radiographic evidence of viable disease regardless of any change in tumor diameter.

A biopsy is recommended in the case of tumors with ≥4mm increase in size with no radiographic evidence of viable tumor, OR any tumors with radiographic evidence of viable tissue.

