## 9.0 STATISTICAL CONSIDERATIONS

### 9.1 Study Design/Study Endpoints

This is an open label single-arm phase II non-randomized prospective single arm study that treats a single SRM with SABR. The primary objective is local control of the SRMs. Local control is defined as less than 4mm increase in the longest diameter of tumor measured using either MRI or contrast enhanced CT scan and with no radiographic or pathologic evidence of viable tumor. The endpoint will be measured at a minimum follow up of one year. Secondary objections and endpoints explore the safety, toxicity, growth, growth rate, local failure, IDR, immune response and progression of the SRMs after SABR.

The stopping rules for this study include any treatment-related >grade 3 toxicity. If there are any treatment related grade 3 acute toxicity in >30% of enrolled patients after enrollment of at least 6 patients, the study will be suspended until permitted by a safety review.

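### Non-contrast MRI is allowed throughout but has no scoring rule for radiographic viability, so local control may be overstated in a limited group of patients

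*Protocol*

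**What the plan says.** **Imaging.** Baseline (section 5.1.15): "Tumor assessment will be performed using MRI with (preferred) or without contrast, or contrast enhanced CT". Follow-up (section 5.3): "MRI with or without contrast or CT with contrast". Technique (section 6.1.3): "MRI: Will be performed with gadolinium if possible". CT must be contrast-enhanced; MRI need not be. Section 6.1.3 adds: "The same method of assessment and the same technique should be used to characterize each identified and reported lesion at baseline and during follow-up". A patient who starts without contrast would therefore be expected to continue without it.

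**Endpoint.** Section 2.4.1 requires limited growth "in the setting of no radiographic or pathologic evidence of viable tumor". Section 9.1 repeats this, with the tumour "measured using either MRI or contrast enhanced CT scan and with no radiographic or pathologic evidence of viable tumor", and sets one year as the minimum follow-up. Section 6.1.4.1 defines Local Control as "No TG AND a complete radiographic or pathologic absence of tumor viability", while its Local Failure line counts either kind of evidence as failure. The rationale (section 1.3) mentions radiographic viability only.

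**Biopsy.** Section 5.1.14.2 requires a one-year biopsy whether a "clinical indication (tumor growth >4mm, enhancement, etc.) is present or not". Section 6.2 judges pathologic response on that biopsy.

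**Who is kept.** Section 3.1.6 asks only that a patient can have an MRI or receive CT contrast. The evaluability definition (6.1.1) does not mention the biopsy, and a missing biopsy is not a reason for replacement (4.13).

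**The concern.** The primary objective (section 2.1.1) is to eliminate both growth and viable tumour. Enhancement is a sign of residual disease that the protocol names itself (5.1.14.2), and the percentage of enhancement is a listed radiographic measure (2.2.5). Neither can be read without contrast. The protocol does not say how viability is judged on such a scan, or that it cannot be judged. A sign that was not looked for is then recorded in the same way as a sign that was looked for and not found.

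Any resulting error in the radiographic component goes one way, toward local control. The patients concerned are foreseeable: section 4.5.1, on the planning CT, already recognises contrast allergy and renal insufficiency as reasons to omit contrast. Because such patients can still have an MRI, they are enrolled, evaluable and not replaced.

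**Working it through.** **1. The plan's own precision.** Section 9.2 gives n = 16, an expected rate of at least 90%, a standard error of at most 7.5% and a 95% interval of 15%.

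SE = √(0.90 × 0.10 / 16) = 7.5%; 1.96 × 7.5% = 14.7%. This reproduces, reading 15% as the half-width. The contrast issue does not alter it.

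**2. One patient.** 1/16 = 6.25 points. For example, 14/16 = 87.5% (exact 95% CI 61.7 to 98.4) against 15/16 = 93.8% (69.8 to 99.8).

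**3. Where a clean non-contrast scan can lead to a wrong call**

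| Situation | What the protocol does |
|---|---|
| One-year biopsy positive | Local Failure (6.1.4.1); corrected |
| Biopsy missing or non-diagnostic | Still evaluable (6.1.1), not replaced (4.13); can be scored as control |
| Biopsy falsely negative | Nothing further; 6.2 needs proliferation shown against pre-treatment tissue |
| Status judged after one year | No biopsy scheduled; the one recommended in 6.1.4.1 needs growth or radiographic evidence of viable tissue |
| *Or* in the Local Control line applied literally | Radiographic absence can stand alone, even beside a positive biopsy |

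**4. Expected bias when the biopsy counts.** All inputs in this step are assumptions; the protocol gives none of them.

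- v: share of non-growing tumours that are viable
- m: share of patients scanned without contrast
- s1, s0: imaging sensitivity with and without contrast
- b: biopsy sensitivity

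With independent errors and no false positives:

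apparent control = (1 − v) + v(1 − b)[(1 − m)(1 − s1) + m(1 − s0)]

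Subtracting the all-contrast case (m = 0) gives:

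bias = v × (1 − b) × m × (s1 − s0)

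With s1 = 0.90 and s0 = 0, the setting least favourable to non-contrast MRI, the bias in points is:

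| v | m | b = 0.70 | b = 0.90 | b = 1.0 |
|---|---|---|---|---|
| 0.10 | 25% | 0.7 | 0.2 | 0 |
| 0.10 | 50% | 1.3 | 0.4 | 0 |
| 0.10 | 100% | 2.7 | 0.9 | 0 |
| 0.20 | 25% | 1.3 | 0.4 | 0 |
| 0.20 | 50% | 2.7 | 0.9 | 0 |
| 0.20 | 100% | 5.4 | 1.8 | 0 |

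Example: 0.20 × 0.30 × 1 × 0.90 = 5.4 points. If non-contrast sequences detect half of viable tumours (s0 = 0.5), the b = 0.70 column for v = 0.20 falls to 0.6, 1.2 and 2.4. At v = 0.30, m = 100%, b = 0.70 and s0 = 0 it reaches 8.1.

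**5. If the biopsy does not count** (b = 0, the literal *or*). With v = 0.20, s1 = 0.90 and s0 = 0, apparent control is 82.0% with contrast in everyone. It becomes 86.5%, 91.0% and 100% for m = 25%, 50% and 100%.

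**The case against.** The strongest case against has four parts.

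- **The endpoint is not radiographic alone.** Sections 2.4.1 and 9.1 and the Local Failure definition count pathologic evidence as well, and every patient is due a biopsy at one year, the earliest time at which the endpoint is measured. This stands. A reader might infer that a patient scanned without contrast meets the viability part by default; the documents do not support that, because a positive biopsy makes the patient a failure.
- **Enhancement is not the only sign.** Section 5.1.14.2 gives an open list, and section 2.2.5 includes T2 signal and diffusion-weighted imaging, which need no contrast. This stands in part. Such sequences can yield positive evidence, but no rule says that a negative reading on them establishes absence of viability.
- **The effect is small.** A reader might reach 6 to 16 points by supposing that 2 to 5 of 16 patients are scanned without contrast and half of them have residual enhancement (1 to 2.5 patients). That gives the biopsy no detection at all and sits badly with section 9.2, which expects at least 90% control. At 10% viable, 2 to 5 patients yield 0.2 to 0.5 misses, or 1.3 to 3.1 points before biopsy. With biopsy sensitivity assumed at 0.70, the figure is about 0.4 to 0.9 points. This stands.
- **The *or* is a separate defect.** It also affects patients imaged with contrast. True, but it matters here because it allows a clean non-contrast scan to override the biopsy. Section 6.1.4.1 is unsettled further by its Indeterminate Disease Response category, which also takes in lesions with no radiographic evidence of viability whatever their change in size.

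**Conclusion.** The gap is real and its reach is limited. Non-contrast MRI is permitted at baseline and every follow-up, cannot show enhancement, and is nowhere made non-evaluable for viability. Local control **may** be biased upward for three groups:

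- patients scanned without contrast whose one-year biopsy is missing, non-diagnostic or falsely negative;
- patients scanned without contrast and assessed after one year;
- any patient scored under the *or* in the Local Control definition.

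The required biopsy corrects most other cases, so an established upward bias in the rate as a whole cannot be claimed.

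The size is unknown, because the protocol gives neither the share scanned without contrast nor any sensitivity. Under the assumptions above (10 to 20% viable, biopsy sensitivity 0.70 to 0.90, 25 to 100% without contrast, no detection without contrast), it is roughly 0.2 to 5 points, and zero if the biopsy is perfect. Patients without a biopsy result, or scored with the biopsy disregarded, do not have that protection. With 16 patients, one such error moves the rate by 6.25 points. This should be fixed, but the trial's interpretation does not hinge on it.

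**What to change.** 1. In sections 2.4.1, 6.1.4.1 and 9.1, define Local Control as no growth and **neither** radiographic **nor** pathologic evidence of viable tumour. Reconcile the Local Control line with the Local Failure line and remove the overlap with Indeterminate Disease Response. Align the sentence in section 1.3.
2. Allow absence of radiographic viability to be scored only on contrast-enhanced MRI or CT. If no contrast was given, code this component as not assessable. A positive sign on T2 or diffusion still counts as evidence of viability, and the scan still counts for diameter.
3. For patients coded not assessable, classify viability by the one-year biopsy already required.
4. Do not count a patient with neither a contrast scan nor a diagnostic biopsy as a local control.
5. Report the number of patients in each category.

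**Cost.** Changes to protocol and case report form wording, with no added scan or biopsy. The local control rate may come out slightly lower, and a few patients may remain unclassified.
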